4.2. Scientific Rationale for Study Design

This is an open-label, single-dose, 4-period crossover study to compare the relative BA of the GSK3640254 formulation planned for Phase 2b (mesylate salt in a tablet) with the Phase 2a formulation (mesylate salt in a capsule) when administered following a moderate calorie and fat meal. In addition, this study will investigate the effect of food on the PK of the GSK3640254 mesylate tablet formulation.

The effect of food on the PK of a structurally similar HIV-1 MI (GSK3532795) was previously evaluated: AUC increased 1.8-, 2.1-, and 2.5-fold when a single dose of 180 mg GSK3532795 was given with a light, moderate, or high fat meal, respectively, as compared to administration under fasting conditions [GSK Document Number [2017N322200_00](#)]. All GSK3640254 clinical studies to date, including a Phase 2a proof of concept study, have been conducted with moderate calorie and fat meals. It is intended that this will be the only food-effect BA clinical study for GSK3640254; therefore, this study will investigate the effect of moderate and high calorie and fat meals on the PK, safety, and tolerability of the GSK3640254 mesylate tablet formulation, as compared to administration under fasting conditions.

The open-label crossover design of this study is well-established for evaluation of the relative BA of different oral dosage forms and for studying the effect of food on BA. Random assignment to treatment sequences is an attempt to prevent bias. The washout of at least 7 days between each dose of study intervention should eliminate the possibility of carryover of drug exposure from the previous dose. There are appropriately named “test” and “reference” study treatments, which will be evaluated for the relative BA comparisons.

This study is participant to the appropriate regulatory and ethics committee approval and will be listed on the website ClinicalTrials.gov. No blinding or placebo control will be used, as these are not necessary for the purposes of this study.

4.3. Justification for Dose

The dose of 200 mg GSK3640254 was selected for this study as the maximum projected clinically therapeutic dose of GSK3640254 is 200 mg QD. The $t_{1/2}$ of GSK3640254 was approximately 22 hours in the MAD portion of Study 207187 at the 200-mg dose. To ensure adequate washout, there will be at least 7 days between each dose of study intervention, with an allowance window of 4 hours (i.e., 7 days minus 4 hours) to allow flexibility in scheduling participants for dosing at the clinic.

4.4. End-of-Study Definition

A participant is considered to have completed the study if he or she has completed all phases of the study including the final date on which data were or are expected to be collected.

The end of the study is defined as the date of the last visit of the last participant in the study or last scheduled procedure shown in the SoA (Section 1.3) for the last participant in the study.

5. STUDY POPULATION

Prospective approval of protocol deviations to recruitment and enrollment criteria, also known as protocol waivers or exemptions, is not permitted.

5.1. Inclusion Criteria

Participants are eligible to be included in the study only if all the following criteria apply:

Age

1. Participant must be 18 to 55 years of age inclusive, at the time of signing the informed consent.

Type of Participant and Disease Characteristics

2. Participants who are healthy as determined by the investigator or medically qualified designee based on a medical evaluation including medical history, physical examination, laboratory tests, and cardiac monitoring (history and ECG).

Weight

3. Body weight ≥ 50.0 kg (110 lbs) for men and ≥ 45.0 kg (99 lbs) for women and body mass index within the range 18.5 to 31.0 kg/m² (inclusive).

Sex

Contraceptive use by men or women should be consistent with local regulations regarding the methods of contraception for those participating in clinical studies.

4. Male or female

- a. Female participants:

1. A female participant is eligible to participate if she is not pregnant or breastfeeding, and at least 1 of the following conditions applies:
 - Is not a woman of childbearing potential (WOCBP) as defined in [Appendix 3](#).OR
 - Is a WOCBP and using a nonhormonal contraceptive method that is highly effective, with a failure rate of <1%, as described in [Appendix 3](#) for 28 days before intervention, during the intervention period, and for at least 28 days after the last dose of study intervention. The investigator should evaluate the effectiveness of the contraceptive method in relationship to the first dose of study intervention.
2. A WOCBP must have a negative highly sensitive serum pregnancy test ([Appendix 2](#)) at Screening and Day -1.
3. Additional requirements for pregnancy testing during and after study intervention are outlined in [Appendix 2](#).

The investigator is responsible for review of medical history, menstrual history, and recent sexual activity to decrease the risk for inclusion of a woman with an early undetected pregnancy.

Informed Consent

5. Capable of giving signed informed consent as described in [Appendix 4](#), which includes compliance with the requirements and restrictions listed in the informed consent form (ICF) and in this protocol.

5.2. Exclusion Criteria

Participants are excluded from the study if any of the following criteria apply:

Medical History

1. Current or chronic history of liver disease or known hepatic or biliary abnormalities (with the exception of Gilbert's syndrome or asymptomatic gallstones).
2. A pre-existing condition interfering with normal GI anatomy or motility (e.g., gastroesophageal reflux disease, gastric ulcers, gastritis), hepatic and/or renal function, that could interfere with the absorption, metabolism, and/or excretion of the study intervention or render the participant unable to take oral study intervention.
3. Any history of significant underlying psychiatric disorder, including, but not limited to, schizophrenia, bipolar disorder with or without psychotic symptoms, other psychotic disorders, or schizotypal (personality) disorder.
4. Any history of major depressive disorder with or without suicidal features, or anxiety disorders that required medical intervention (pharmacologic or not) such as hospitalization or other inpatient treatment and/or chronic (>6 months) outpatient treatment. Participants with other conditions such as adjustment disorder or dysthymia that have required shorter term medical therapy (<6 months) without inpatient treatment and are currently well-controlled clinically or resolved may be considered for entry after discussion and agreement with the VH/GSK Medical Monitor.
5. Any pre-existing physical or other psychiatric condition (including alcohol or drug abuse), which, in the opinion of the investigator (with or without psychiatric evaluation), could interfere with the participant's ability to comply with the dosing schedule and protocol evaluations or which might compromise the safety of the participant.
6. Medical history of cardiac arrhythmias, prior myocardial infarction in the past 3 months, or cardiac disease or a family or personal history of long QT syndrome.

Laboratory Assessments

7. Presence of hepatitis B surface antigen at Screening or within 3 months prior to starting study intervention.
8. Positive hepatitis C antibody test result at Screening or within 3 months prior to starting study intervention AND positive on reflex to hepatitis C ribonucleic acid (RNA).
9. Positive HIV-1 and -2 antigen/antibody immunoassay at Screening.

10. ALT $>1.5 \times$ upper limit of normal (ULN). A single repeat of ALT is allowed within a single Screening period to determine eligibility.
11. Bilirubin $>1.5 \times$ ULN (isolated bilirubin $>1.5 \times$ ULN is acceptable if bilirubin is fractionated and direct bilirubin $<35\%$). A single repeat of any laboratory abnormality is allowed within a single Screening period to determine eligibility.
12. Any acute laboratory abnormality at Screening which, in the opinion of the investigator, should preclude participation in the study of an investigational compound.
13. Any Grade 2 to 4 laboratory abnormality at Screening, with the exception of creatine phosphokinase (CPK) and lipid abnormalities (e.g., total cholesterol, triglycerides), and ALT (described above), will exclude a participant from the study unless the investigator can provide a compelling explanation for the laboratory result(s) and has the assent of the sponsor. A single repeat of any laboratory abnormality is allowed within a single Screening period to determine eligibility.
14. A positive test result for drugs of abuse (including marijuana), alcohol, or cotinine (indicating active current smoking) at Screening or before the first dose of study intervention.

Prior/Concomitant Therapy

15. Unable to refrain from the use of prescription or nonprescription drugs including vitamins, herbal and dietary supplements (including St John's wort) within 7 days (or 14 days if the drug is a potential enzyme inducer) or 5 half-lives (whichever is longer) prior to the first dose of study intervention and for the duration of the study. (Note: acetaminophen/paracetamol at doses of ≤ 2 grams/day and topical hydrocortisone cream 1% are permitted for use any time during the study.)
16. Treatment with any vaccine within 30 days prior to receiving study intervention.
17. Unwillingness to abstain from excessive consumption of any food or drink containing grapefruit and grapefruit juice, Seville oranges, blood oranges, or pomelos or their fruit juices within 7 days prior to the first dose of study intervention(s) until the end of the study.

Prior/Concurrent Clinical Study Experience

18. Participation in another concurrent clinical study or prior clinical study (with the exception of imaging trials) prior to the first dosing day in the current study: 30 days, 5 half-lives, or twice the duration of the biological effect of the study intervention (whichever is longer).
19. Where participation in the study would result in donation of blood or blood products in excess of 500 mL within 56 days.

Diagnostic Assessments

20. Any positive (abnormal) response confirmed by the investigator on a screening clinician- or qualified designee-administered C-SSRS.

21. Any significant arrhythmia or ECG finding (e.g., prior myocardial infarction in the past 3 months, symptomatic bradycardia, non-sustained or sustained atrial arrhythmias, non-sustained or sustained ventricular tachycardia, second-degree atrioventricular block Mobitz Type II, third-degree atrioventricular block, complete heart block, or conduction abnormality) which, in the opinion of the investigator or VH/GSK Medical Monitor, will interfere with the safety for the individual participant.
22. Exclusion criteria for Screening ECG (a single repeat is allowed for eligibility determination):

	Males	Females
Heart rate ¹	<45 or >100 bpm	<50 or >100 bpm
QTcF interval ² (Fridericia's)	>450 ms	>450 ms

- 1 A heart rate from 100 to 110 bpm can be rechecked by electrocardiogram or vital signs within 30 minutes to verify eligibility.
- 2 The QTc is the QT interval corrected for heart rate using Fridericia's formula (QTcF). It is either machine read or manually over-read. The specific formula used to determine eligibility and discontinuation for an individual participant will be Fridericia's formula.

Other Exclusions

23. History of regular alcohol consumption within 6 months of the study defined as an average weekly intake of >14 units. One unit is equivalent to 8 g of alcohol: a half-pint (~240 mL) of beer, 1 glass (125 mL) of wine, or 1 (25 mL) measure of spirits.
24. Unable to refrain from tobacco or nicotine-containing products within 3 months prior to Screening.
25. History of sensitivity to any of the study medications, or components thereof or a history of drug or other allergy that, in the opinion of the investigator or medical monitor, contraindicates their participation.

5.3. Lifestyle Considerations

5.3.1. Meals and Dietary Restrictions

- Refrain from excessive consumption of red wine, grapefruit and grapefruit juice, Seville oranges, blood oranges, or pomelos or their fruit juices within 7 days prior to the first dose of study intervention(s) until the end of the study. Excessive consumption is defined as more than one glass of wine or juice or one of these fruits per day, in combination.
- Treatments A, B, and D will be administered in the fed state. The participants will fast overnight for at least 10 hours prior to dosing and will receive a moderate fat (Treatments A and B) or high fat (Treatment D) meal 30 minutes prior to dosing. Participants will eat this meal in 30 minutes or less. Dose administration will occur within 5 minutes of completion of meal consumption. Participants will not receive any further food until 4 hours after dosing on serial PK sampling days (e.g., Day 1 of Periods 1, 2, 3, and 4). The moderate fat meal will contain about 600 calories with approximately 30% of the calories coming

from fat. The high fat meal will contain about 800 to 1000 calories with approximately 50% of the calories coming from fat (DHHS, 2002).

- Treatment C will be administered in the fasted state. The participants will fast overnight for at least 10 hours prior to dosing until 4 hours after dosing.
- No water is allowed from 1 hour prior to dosing until 1 hour after dosing except for the glass of water needed to administer the study intervention (e.g., 240 mL). Water is allowed ad libitum at all other times.
- A standard lunch will be provided 4 hours after dosing. A standard dinner will be served approximately 10 hours after dosing. The food content of meals must be identical on serial PK sampling days (e.g., Day 1 of Periods 1, 2, 3, and 4).

5.3.2. Caffeine, Alcohol, and Tobacco

- Participants will abstain from ingesting caffeine- or xanthine-containing products (e.g., coffee, tea, cola drinks, and chocolate) for 24 hours before the start of dosing until after collection of the final PK sample.
- Participants will abstain from alcohol for 48 hours before the start of dosing until after collection of the final PK sample.
- Use of tobacco and nicotine-containing products will not be allowed from 3 months prior to Screening until after the final visit.
- Participants must have a negative drug test at Screening and Day –1 and must abstain from recreational drug use from Screening until after the final visit.

5.3.3. Activity

- Participants will abstain from strenuous exercise for 24 hours before each blood collection for clinical laboratory tests. Participants may participate in light recreational activities during studies (e.g., watching television, reading).

5.4. Screen Failures

Screen failures are defined as participants who consent to participate in the clinical study but are not subsequently entered in the study. A minimal set of screen failure information is required to ensure transparent reporting of screen failure participants to meet the Consolidated Standards of Reporting Trials (CONSORT) publishing requirements and to respond to queries from regulatory authorities. Minimal information includes demography, screen failure details, eligibility criteria, and any SAEs.

Individuals who do not meet the criteria for participation in this study (screen failure) may not be rescreened.

6. STUDY INTERVENTION

Study intervention is defined as any investigational intervention(s), marketed product(s), placebo, or medical device(s) intended to be administered to a study participant according to the study protocol.

6.1. Study Interventions Administered

Intervention Name	GSK3640254	GSK3640254
Type	drug	drug
Dose Formulation	tablet	capsule
Unit Dose Strength(s)	100 mg	100 mg
Dosage Level(s)	200 mg, single dose	200 mg, single dose
Route of Administration	oral	oral
IMP and NIMP	IMP	IMP
Sourcing	Provided centrally by the Sponsor	Provided centrally by the Sponsor
Packaging and Labeling	Provided in high-density polyethylene bottles. Each bottle will be labelled as required per country requirement.	Provided in high-density polyethylene bottles. Each bottle will be labelled as required per country requirement.

IMP = investigational medicinal product; NIMP = non-investigational medicinal product

6.2. Preparation/Handling/Storage/Accountability

1. The investigator or designee must confirm appropriate temperature conditions have been maintained during transit for all study intervention received and any discrepancies are reported and resolved before use of the study intervention.
2. Only participants enrolled in the study may receive study intervention and only authorized site staff may supply or administer study intervention. All study interventions must be stored in a secure, environmentally controlled, and monitored (manual or automated) area in accordance with the labeled storage conditions with access limited to the investigator and authorized site staff.
3. The investigator, institution, or the head of the medical institution (where applicable) is responsible for study intervention accountability, reconciliation, and record maintenance (i.e., receipt, reconciliation, and final disposition records).
4. Further guidance and information for the final disposition of unused study intervention are provided in the Study Reference Manual (SRM).
5. Under normal conditions of handling and administration, study intervention is not expected to pose significant safety risks to site staff.
6. A Material Safety Data Sheet/equivalent document describing occupational hazards and recommended handling precautions either will be provided to the investigator, where this is required by local laws, or is available upon request from VH/GSK.

6.3. Measures to Minimize Bias: Randomization and Blinding

This is an open-label study. Study participants will be randomly assigned to 1 of 4 treatment sequences (ABCD, BADC, CDAB, or DCBA) in accordance with the randomization schedule generated by PPD prior to the start of the study and using validated software.

6.4. Study Intervention Compliance

- When the individual dose for a participant is prepared from a bulk supply, the preparation of the dose will be confirmed by a second member of the study site staff.
- When participants are dosed at the site, they will receive study intervention directly from the investigator or designee, under medical supervision. The date and time of each dose administered in the clinic will be recorded in the source documents. The dose of study intervention and study participant identification will be confirmed at the time of dosing by a member of the study site staff other than the person administering the study intervention. Study site personnel will examine each participant's mouth to ensure that the study intervention was ingested.

6.5. Concomitant Therapy

Acetaminophen/paracetamol at doses of ≤ 2 grams/day and topical hydrocortisone cream 1% are permitted for use any time during the study and their use should be documented in the case report form (CRF). Other medications are not permitted without prior discussion with the VH/GSK medical monitor.

6.6. Dose Modification

Not applicable.

6.7. Intervention After the End of the Study

Participants will not receive any additional treatment from VH/GSK, or with GSK3640254, after the completion of the study because only healthy participants are eligible for study participation.

7. DISCONTINUATION OF STUDY INTERVENTION AND PARTICIPANT DISCONTINUATION/WITHDRAWAL

7.1. Discontinuation of Study Intervention

In rare instances, it may be necessary for a participant to permanently discontinue study intervention. If study intervention is permanently discontinued, the participant will remain in the study to be evaluated for safety. See the SoA (Section 1.3) for data to be collected at the time of discontinuation of study intervention.

7.1.1. Liver Chemistry Stopping Criteria

Liver chemistry stopping and increased monitoring criteria have been designed to assure participant safety and evaluate liver event etiology (in alignment with the Food and Drug Administration premarketing clinical liver safety guidance:

<https://www.fda.gov/downloads/Drugs/GuidanceComplianceRegulatoryInformation/Guidances/UCM174090.pdf>).

Discontinuation of study intervention for abnormal liver tests is required when a participant has an ALT $\geq 3 \times$ ULN or if the investigator believes study intervention discontinuation is in the best interest of the participant.

Details of liver safety follow-up procedures are described in [Appendix 5](#).

7.1.1.1. Study Intervention Restart or Rechallenge After Liver Stopping Criteria Met

Study intervention restart or rechallenge after liver chemistry stopping criteria are met by any participant in this study is not allowed.

7.1.2. QTc Stopping Criteria

The *same* correction formula (QTcF) *must* be used for *each individual participant* to determine eligibility for and discontinuation from the study. This formula may not be changed or substituted once the participant has been enrolled.

- The Baseline QTcF should be based on averaged QTcF values of triplicate ECGs obtained over a brief (e.g., 5-10 minute) recording period from the Day -1 ECG.
- A randomized participant that develops an on-treatment QTcF >500 ms or an increase from Baseline QTcF >60 ms should have two repeat unscheduled ECGs within 10 minutes. Using these triplicate ECGs, if the average QTcF >500 ms or an increase from Baseline QTcF >60 ms, the participant will be withdrawn from the study. Finally, this participant should have repeated unscheduled ECGs until their QTcF measurement returns to their original averaged QTcF value at Day -1.

See the SoA (Section [1.3](#)) for data to be collected at the time of treatment discontinuation and follow-up and for any further evaluations that need to be completed.

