1.3. Schedule of Activities (SoA)

- Screening procedures may be done over more than 1 visit but must all be completed within 28 days prior to the first dose of study intervention.
- The following demographic parameters will be captured: year of birth, sex, race, and ethnicity.
- Medical/medication/family history will be assessed as related to the inclusion/exclusion criteria.

Screening Visit

Procedure	Screening (up to 28 days before Day 1)
Outpatient visit	X
Informed consent	X
Inclusion and exclusion criteria	X
Demography	X
Full physical examination including height and weight ¹	X
Laboratory assessments (hematology, chemistry, urinalysis)	X
12-lead electrocardiogram	X
Vital sign measurements	X
Medication/drug/alcohol history	X
Past and current medical conditions	X
Columbia Suicide Severity Rating Scale	X
Serum pregnancy test	X
Follicle-stimulating hormone (as needed, to confirm postmenopausal status)	X
Drug, alcohol, and cotinine screen	X
Human immunodeficiency virus, hepatitis B and C Screening	X

¹ A full physical examination will include at a minimum, assessments of the skin, cardiovascular, respiratory, gastrointestinal, and neurological systems.

Time and Events Table

Procedure	Check-in	Periods 1, 2, and 3				Period 4 only				Notes
		Day -1	Day 1	Washout		Day 1	Day 2	Days 3-4	Day 5 ¹	
				Day 2	Days 3-5					
Admit to clinic	X									
Discharge from clinic									X	Discharge from clinic following completion of the last study procedure on Day 5 of Period 4.
Brief physical examination	X				D7 (Period 2 only)				X	Interim or symptom targeted physical examination will be performed at the discretion of the investigator. See Section 8.2.1 for description of brief physical examination.
Vital signs	X	X	X	D3-5		X	X	X	X	Blood pressure and pulse will be measured in triplicate predose on Day 1 in Periods 1-4. Single blood pressure and pulse will be measured predose on other study days.
12-lead ECG	X	X				X			X	All ECGs on Day 1 in Periods 1-4 will be predose, postdose at 2 hours, and postdose at 4 hours. The predose ECGs in Periods 1-4 will be taken in triplicate.
Drug, alcohol, and cotinine screen	X									See Appendix 2 for specific tests to be performed.
Laboratory assessments (hematology, chemistry, urinalysis)	X		X				X		X	See Appendix 2 for specific tests to be performed. Day 2 samples in each period to be collected 24 hours after dosing.

Procedure	Check-in	Periods 1, 2, and 3				Period 4 only				Notes	

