8.2. Safety Assessments

Planned time points for all safety assessments are provided in the SoA (Section 1.3).

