8.2.3. Electrocardiograms

- Twelve-lead ECGs will be obtained using an ECG machine that automatically calculates the heart rate and measures PR, QRS, QT, and QTcF intervals. Refer to Section 7.1.2 for QTcF withdrawal criteria and additional QTcF readings that may be necessary.
- Twelve-lead ECGs will be performed with the participant in a supine or semi-supine position after a rest of at least 10 minutes.

- At each time point at which triplicate ECGs are required, 3 individual ECG tracings should be obtained as closely as possible in succession, but no more than 2 minutes apart. The full set of triplicates should be completed over a brief (e.g., 5 to 10 minutes) recording period. Each measurement will be recorded in the CRF.

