5.2. Baseline Definitions

For vital signs and 12-lead ECGs, the baseline value will be the average (for quantitative assessments) or the worst case (for interpretation) of the triplicate predose assessments within each period. For clinical laboratory parameters, the baseline value will be the latest pre-dose assessment with a non-missing value, including those from unscheduled visits, before the first dose of study drug administration. If time is not collected, Day 1 assessments within each period are assumed to be taken prior to the dose and used as baseline.

Parameter	Study Assessments Considered as Baseline			Baseline Used in Data Display
	Screening	Day -1	Day 1 (Pre-Dose)	
Safety				
Vital Sign	X	X	X	Day 1 (Pre-Dose) ^[1] for each period
12-Lead ECG	X	X	X	Day 1 (Pre-Dose) ^[1] for each period
Hematology	X	X		Day -1
Clinical Chemistry	X	X		Day -1
Urinalysis	X	X		Day -1

ECG = Electrocardiogram.

[1] The average (for quantitative assessments) or the worst case (for interpretation) of the predose triplicate assessments will be used as the baseline.

Unless otherwise stated, if baseline data is missing no derivation will be performed and baseline will be set to missing.

CONFIDENTIAL

209713

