10.4.3. Safety

Adverse Events
AEs of Special Interest

 • QT prolongation • Gastrointestinal intolerability/toxicity • Psychiatric events • Nervous system disorders

12-Lead Electrocardiograms
QTcB Interval

 • QTc using the Bazett formula (QTcB) interval in msec will be calculated using QT interval (msec) and RR (msec) as $QT_{cB} = \frac{QT}{\sqrt{\frac{RR}{1000}}}$ 
where RR interval in msec is calculated using QT interval (msec) and QTcF interval (msec) as
 $RR = \left(\frac{QT}{QT_{cF}}\right)^3 \times 1000$

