10.7. Appendix 7: Values of Potential Clinical Importance**10.7.1. ECG**

ECG Parameter	Units	Potential Clinically Important Range	
		Lower	Upper
Absolute			
Absolute QTc Interval	msec	<320	>450
Absolute PR Interval	msec	< 120	> 200
Absolute QRS Interval	msec	< 60	> 120
Change from Baseline			
Increase from Baseline QTc	msec		> 60

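### Does the QTcF stopping rule lean on a Day -1 triplicate that the schedule never orders, and does the SAP's different ECG baseline matter?

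*Protocol*

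**What the plan says.** **Stopping rule.** Protocol 7.1.2 says "The Baseline QTcF should be based on averaged QTcF values of triplicate ECGs", taken from the Day -1 ECG. An on-treatment QTcF above 500 ms, or more than 60 ms above baseline, prompts two repeat ECGs. If the average of the three still breaches either limit, the participant is withdrawn and followed until QTcF "returns to their original averaged QTcF value at Day -1".

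**Schedule.** Protocol 8.2 says "Planned time points for all safety assessments are provided in the SoA". The schedule in Protocol 1.3, copied in SAP 10.1.1, marks a 12-lead ECG at the Day -1 check-in. Its only statement about replicates is "The predose ECGs in Periods 1-4 will be taken in triplicate". Protocol 8.2.3 gives the technique, opening with "At each time point at which triplicate ECGs are required", and names no days. Its first bullet does send the site to 7.1.2 for the QTcF withdrawal criteria.

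**SAP.** Section 5.2 takes the ECG baseline as the average "of the triplicate predose assessments within each period". Appendix 7 (10.7.1) sets a limit of 60 msec for "Increase from Baseline QTc" and names neither a baseline nor a correction formula, while 10.4.3 adds that "QTc using the Bazett formula (QTcB) interval in msec will be calculated". The table of changes in SAP 2.1 does not mention the ECG baseline.

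**The concern.** QTc prolongation is one of the major risks named in Protocol 2.3. Clinic staff tend to work from the schedule. A reader of the schedule alone could take one Day -1 tracing, and the stopping rule would then rest on a noisier reference than 7.1.2 intends. Noise in that reference can cause a needless withdrawal or hide a real increase.

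The SAP repeats the 60 ms threshold, but its only ECG baseline is reset in each period. The same words therefore describe two quantities. An increase counted under SAP 10.7.1 need not be one judged under 7.1.2, and the SAP does not say so. Appendix 9 plans listings of potentially important values for vital signs (Listings 31 and 32) but has no ECG counterpart.

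**Working it through.** The plan gives no figure to reproduce here, so the check compares the sections and then sizes the worst reading.

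**1. Can the protocol sections be followed together?** Section 7.1.2 supplies the day and the number of tracings. The schedule supplies the day. Section 8.2.3 supplies the technique and points to 7.1.2. Nothing asks for a single ECG on Day -1. The same schedule does say single for blood pressure and pulse outside Day 1, and says no such thing for ECGs. Following all the sections yields the Day -1 triplicate.

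**2. What if one tracing was taken?** Let s be the SD between replicates and b the SD between days. Neither is in the documents. Readings are assumed independent, and the confirmatory value is a mean of three.

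- Triplicate baseline: SD of change = sqrt(s²/3 + s²/3 + 2b²) = sqrt(2s²/3 + 2b²)
- Single baseline: SD of change = sqrt(s²/3 + s² + 2b²) = sqrt(4s²/3 + 2b²)

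| s (ms) | b (ms) | Triplicate | Single | Increase |
|---|---|---|---|---|
| any | 0 | 0.82s | 1.15s | 41% |
| 8 | 3 | 7.79 | 10.17 | 30.5% |
| 8 | 8 | 13.06 | 14.61 | 11.8% |
| 4 | 8 | 11.78 | 12.22 | 3.8% |

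The 41% needs b = 0. It is an upper bound, because baseline and on-treatment ECGs fall on different days.

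**3. How close is 60 ms?** Protocol 2.2.2 and 2.3 predict 5.38 ms (90% CI 1.66 to 9.10) at 200 mg on Day 14, and no participant in the first-in-human study exceeded 60 ms. In the noisiest assumed case the threshold lies (60 - 5.38)/14.61 = 3.7 SDs above that prediction with a single baseline, and 54.62/13.06 = 4.2 SDs with a triplicate. Day 14 peak concentrations were 1.9 to 2.3 times those of Day 1, so a single dose under the moderate fat meal used then should do less. The high fat meal had not been studied.

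**4. How far apart are the two baselines?** With both in triplicate, their difference has SD sqrt(2s²/3 + 2b²). This is 5.35 ms (s = 4, b = 3) to 13.06 ms (s = b = 8), so they differ by more than 10 ms in about 6% to 44% of participant-periods. A hypothetical case: Day -1 405, predose 415 and postdose 470 ms give +65 under the rule and +55 under the SAP. Carryover adds little. The washout is 7 × 24 - 4 = 164 h, and with half-lives of 22 to 29 h the residue is 2^(-164/22) = 0.6% to 2^(-164/29) = 2.0%.

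**5. Where would the SAP baseline show?** It enters Table 2.12 and Figure 2.1, both change-from-baseline summaries for which a period baseline is suitable. No display in Appendix 9 is titled for the 10.7.1 ECG limits. SAP 8.4 and Figure 2.1 both name QTcF, so the unnamed formula in 10.7.1 does not affect the QTc change figure.

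**6. Can a breach of the rule be traced?** A confirmed breach means withdrawal, which falls under Listing 2 (reasons for study withdrawal). Listing 30 gives all ECG values. SAP 10.3.2 keeps unscheduled readings in listings, and 10.4.1 presents every one of multiple measurements when data are listed. The number of Day -1 tracings and any unconfirmed trigger can therefore be read there.

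**The case for a change.** The case for a change is that a safety rule should not depend on a site reading two sections together, and that one threshold should not carry two meanings in one study. The remedy would be cheap: a few SAP sentences and one listing from data in hand, about (2 periods × 2 postdose ECGs + 1 early-discontinuation ECG) × 16 = 80 scheduled readings if the planned 16 participants were dosed. SAP Table 1 already records a Randomized population for which its protocol column shows no entry, so noting the baseline there would not be out of place.

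Part of this stands. The schedule would be clearer with a replicate count for Day -1. A sentence in SAP 5.2 separating the analysis baseline from the stopping baseline, and a named formula in 10.7.1, would spare a reader some work.

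The rest does not. Table 1 is for changes to the planned statistical analysis. Section 7.1.2 is a conduct rule, Protocol section 9 defines no ECG analysis baseline, and 9.4.2 leaves safety detail to the analysis plan. The extra listing would rearrange values that Listing 30 already shows, in a report that SAP section 1 deliberately abbreviates after early termination. SAP 3.1 records that all participants had completed Period 2 when the study stopped, so new wording in the schedule could no longer affect any tracing.

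**Conclusion.** No change to the plan follows. The protocol leaves a detail out of one table and states it in another section, and read as a whole it delivers the baseline that the rule needs. The SAP's per-period baseline is a fair choice for a crossover. It plays no part in the decision to withdraw and does not touch the primary pharmacokinetic analysis. The limb of the rule at 500 ms needs no baseline at all.

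The possible cost is confined to a site that recorded one Day -1 tracing despite 7.1.2. The SD of the confirmatory change would then rise by at most 41%, or by about 4% to 30% with assumed replicate SDs of 4-8 ms and between-day SDs of 3-8 ms. These figures also assume independent readings. Which baseline should govern stopping is for the sponsor. If the documents are reopened for other reasons, 7.1.2 and the schedule could be worded alike, but no analysis or conclusion depends on it.
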